#### **16. Investigator's Responsibilities and Qualifications**

##### **16.1 General Responsibilities**

The role of the investigator is to implement and manage the day-to-day conduct of the clinical investigation and to ensure data integrity and the rights, safety and well-being of the subjects

involved in the clinical investigation. The participating institution shall appoint an appropriately qualified person to be the site principal investigator.

Prior to subject enrolment the investigational center must have Institutional review board approval for the study.

Investigators shall be qualified by education, training and experience to assume responsibility for the proper conduct of the clinical investigation. Investigators shall disclose potential conflicts of interest, including financial, that interfere with the conduct of the clinical investigation or interpretation of the results. Investigators shall be knowledgeable with the method of obtaining informed consent.

The Investigator shall ensure compliance with the applicable regulatory requirements and ethical

principles for the process of obtaining informed consent. All protocol deviations should be recorded on the Protocol deviation form.

## 17 Data handling and record keeping

### 17.1 Confidentiality

Patient confidentiality will be strictly maintained. Patients will be assigned a Study ID.

Access to patient records will be limited to the study group and the Investigator-

delegated study

coordinator.

### 17.2 Data Management

Dedicated software and electronic database and the case report forms (eCRF) will be used to host the Clinical Trial data for this study. The database is developed and utilized in accordance with

international requirements and standards applicable to clinical investigations i.e. Good Clinical

Practice (GCP) and is a GCP compliant environment meeting applicable 21 CFR Part 11 requirements.

## 18. Case Report Forms

The electronical Case Report Forms (eCRF) and software are the primary data collection instruments for the study.

All data requested on the eCRFs will be recorded. All missing data will be explained.

## 19. Sample Size and Statistical Analysis

### 19.1 Sample size

To calculate a sample size needed to compare these two groups we estimated a 10 % rate of IH in mesh group and 25 % IH in control group on clinical assessment and ultrasound examination.

Assuming  $\alpha = 0.05$  and power = 80%, we would need 97 patients per group. Further, assuming a 2- year dropout rate of 20%, 122 patients per group are needed (totally 244 patients). The sample

size is calculated only for the primary outcome, the secondary outcomes will be interpreted as

hypothesis generating only. If the estimated 20% dropout rate exceeds, the sample size may be recalculated.

All analyses will be performed by or under the guidance of professional statistician and following the CONSORT guidelines.

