	
 
• Incisional hernia repair rate within 2 and 5 years after surgery
 
• Re-operations due to mesh- or hernia within 2 and 5 years from surgery
 
• Quality of life (RAND-36, AAS, PROMIS) within 30 days, 2 and 5 years from surgery
 
• Medico-economic explorative measures 
 
◦ Time to create the retrorectal space and insert the mesh
 
◦ Length of stay
 
◦ Costs of materials used to close the abdomen
 
◦ Length of sick leave
 
 
 

	
At least 244 subjects will be enrolled in this study (122 per group, including 20% off lost to follow-up during 2 years interval).
 
All patients undergoing midline emergency laparotomy during the enrollment period will be screened for inclusion and exclusion criteria and recorded at study sites in order to identify any selection bias.

Randomization	
Patients having emergency midline laparotomy for any gastrointestinal indication and fulfilling the inclusion criteria, will be randomized prior to surgery after giving informed consent to the study.
 
Patients are randomly allocated (1:1 ratio) either to an intervention group or a control group according to a computer-generated list compiled by a biostatistician otherwise uninvolved in the clinical care of trial patients.
 
Allocation will be stratified according to BMI (<30 and <math>\geq 30\text{kg/m}^2</math>), history of previous midline laparotomy and age (<65 and <math>\geq 65</math>- years) and blocked within strata using random permuted blocks (block size 2, 4, 6 and 8). A separate randomization list will be created for each participating center.

Total Study Duration	
Approximately 7-8 years:
 
 
• Site start-up: 3 months
 
• Study Enrollment: 24 months
 
• Short term follow-up: Discharge, 30 days
 
• Long term follow-up: 2 years and 5 years
 

Inclusion/ Exclusion Criteria	
Study Inclusion:
 
 
• Midline emergency laparotomy for any gastrointestinal indication
 
 
Study Exclusion:

Number of  
Patients

- Previous ventral hernia repair with mesh in the midline
  - Previous inguinal or femoral hernia repair by any technique with mesh is accepted
- Previous WHO class of physical activity 3-4 (WHO 3 more than 50% of time at rest, WHO 4 stays at rest most of the time)
- Relaparotomy

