### 7.2 Exclusion Criteria

- Previous ventral hernia repair with mesh in the midline
  - Previous inguinal or femoral hernia repair by any technique with mesh is accepted
- Previous WHO class of physical activity 3-4 (WHO 3 more than 50% of time at rest, WHO 4 stays at rest most of the time)
- Relaparotomy
- Indication for laparotomy is incarcerated hernia
- Pregnant or suspected pregnancy
- <18 years
- Metastatic malignancy of any origin
- Planned Ostomy
- Patients living geographically distant and/or unwilling to return for follow-ups
- No informed consent
- Subject participates in another RCT

Intra-operative exclusion criteria applicable for both randomization groups

- Abdomen is left open
- Second look laparotomy planned
- Inability to keep the mesh securely out of the peritoneal cavity or close the anterior fascia
- Intra-abdominal malignancy diagnosed at the operation
- >2 cm hernia in midline
- Ostomy made at the operation

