### 19.2 Allocation

Patients having emergency midline laparotomy for any indication and fulfilling the inclusion criteria will be randomized prior to surgery after informed consent is signed. Patients are randomly

allocated (1:1 ratio) either to an intervention group or a control group according to a computer-

generated list compiled by a biostatistician otherwise uninvolved in the clinical care of trial patients. Allocation will be stratified according to BMI ( $<30$  and  $\geq 30\text{kg/m}^2$ ), history of previous

laparotomy and age ( $<65$  and  $\geq 65$ - years) and-blocked within strata using random permuted blocks (block size 2, 4, 6 and 8). A separate randomization list will be created for each participating

center. All patients who have an emergency midline laparotomy during randomization period are assessed for eligibility.

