### 19.3 Endpoint analysis

All analyses will be performed primarily according to modified intention to treat (ITT) principle.

Patients who fulfill exclusion criteria intraoperatively (after randomization) will not be included in the analyses. Per protocol analyses will be used as safeguard against the risk of falsely claiming

PREEMER TRIAL 30

equality/superiority. The primary endpoint will be the incidence difference of IHs with 95% confidence interval between the study groups during 2-years follow up. Secondary outcomes are

listed previously. The primary endpoint as well as other categorical data will be analyzed by the  $\chi^2$ - test or Fisher's exact test. Student's t-test or Welch test will be used for continuous variable, the

latter if assumption of homogenous variances does not hold. The incidence of hernia will also be

analyzed using Kaplan-Meier analysis.

The linear mixed model (LMM) or generalized linear mixed model (GLMM) will be used for repeatedly measured data, the previous for continuous data and latter for categorical data. Multiple imputations of missing outcome data will be used for sensitivity analyses.

Prospectively

planned subgroup analyses are as follows: BMI>30, previous hernia and contamination class 4.

However, sample size calculation is done only for the primary end point and subgroup analyses are hypothesis generating only. The statistical programs SPSS (IBM Corp.

Released 2016. IBM SPSS

Statistics for Windows, Version 24.0. Armonk, NY: IBM Corp) and SAS (version 9.4, SAS Institute Inc., Cary, NC, USA) will be used for the analyses.

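### Section 19.1 allows for 20% loss to follow-up but not for patients removed from the analyses after randomisation because of intra-operative exclusion

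*Protocol*

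**What the plan says.** Section 19.1 sets the effect with the words "we estimated a 10 % rate of IH in mesh group and 25 % IH in control group" and continues: "power = 80%, we would need 97 patients per group". It then inflates for attrition: "assuming a 2- year dropout rate of 20%, 122 patients per group are needed (totally 244 patients"). The synopsis says what the inflation covers: "At least 244 subjects will be enrolled in this study (122 per group, including 20% off lost to follow-up during 2 years interval"). The one provision for a larger trial is in 19.1: "If the estimated 20% dropout rate exceeds, the sample size may be recalculated".

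Three other places create a further loss:

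- Section 19.2: patients "will be randomized prior to surgery after informed consent is signed".
- Section 7.2 has a list headed "Intra-operative exclusion criteria applicable for both randomization groups". Its six items are an abdomen left open, a planned second look, a mesh that cannot be kept out of the peritoneal cavity or an anterior fascia that cannot be closed, malignancy found at operation, a midline hernia over 2 cm, and an ostomy made at operation.
- Section 19.3: "Patients who fulfill exclusion criteria intraoperatively (after randomization) will not be included in the analyses".

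**The concern.** The design loses patients at two points, and the sample size allows for one of them. Loss to follow-up takes patients out over two years. Intra-operative exclusion takes them out on the day of surgery, after they have been counted as randomised. The two are separate, and the synopsis wording ties the 20% to the first alone.

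The primary analysis would then run on fewer patients than the power statement assumes. If the trial shows no significant difference, a reader needs to know what power it had, and 19.1 does not provide this: it never states whether 244 is counted before or after intra-operative exclusion.

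**Working it through.** **Inputs from the protocol.** Hernia rates of 10% (mesh) and 25% (control), α = 0.05, power 80% and dropout 20% (section 19.1); 1:1 allocation (section 19.2). Sidedness is not stated. Two-sided is assumed, since the one-sided formula gives 79 per group (92 with continuity correction).

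**Reproducing the plan's figures.** Normal approximation with unpooled variance:

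n = (1.960 + 0.842)² × (0.10 × 0.90 + 0.25 × 0.75) / 0.15² = 7.849 × 0.2775 / 0.0225 = 96.8, so 97 per group.

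Dropout: 97 / 0.8 = 121.25, so 122 per group and 244 in total. Both match.

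**Room left for a second loss.** 122 × 0.8 = 97.6 evaluable per group. The tolerable exclusion rate is 1 − 97/97.6 = 0.6%. In whole patients, 194 must be evaluable: one exclusion leaves 243 × 0.8 = 194.4, and two leave 242 × 0.8 = 193.6, which is short.

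**Effect of an exclusion rate e.** The protocol gives no value for e, so every rate below is an assumption.

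- Evaluable per group = 122 × (1 − e) × 0.8, rounded down.
- Power is by full enumeration of two binomials (0.25 and 0.10) with the uncorrected chi-square test, two-sided 0.05.
- Highest dropout that still leaves 97 = 1 − 97 / (122 × (1 − e)).
- Number to randomise for 97 evaluable after both losses = 2 × ⌈97 / (0.8 × (1 − e))⌉.

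| Assumed e | Evaluable per group | Exact power | Highest dropout leaving 97 | Randomised to keep 97 |
|---|---|---|---|---|
| 0% | 97 | 80.2% | 20.5% | 244 |
| 1% | 96 | 79.7% | 19.7% | 246 |
| 5% | 92 | 77.7% | 16.3% | 256 |
| 10% | 87 | 75.1% | 11.7% | 270 |
| 20% | 78 | 71.6% | 0.6% | 304 |
| 30% | 68 | 64.6% | none (122 × 0.7 = 85.4) | 348 |

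Rounding to the nearest patient changes little: 93 per group at 5% gives about 78%, and 88 at 10% gives about 76%. The unpooled normal formula behind the 97 gives a similar gradient: 78.3%, 76.1%, 71.1% and 65.3% at 5%, 10%, 20% and 30%.

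**The case against.** **244 may be counted after exclusion.** Section 19.1 says the patients are needed and does not say randomised. The synopsis sets 244 as a floor. On that reading no power is lost and the fault is only one of clarity. It fits the rest of the text poorly: the synopsis says 244 will be enrolled, section 4 has all enrolled subjects assessed pre-operatively, and the consent section places enrolment directly after signature. The flow chart in section 10.3 could not be seen in the text reviewed and might bear on this, so nothing here relies on it. A floor also permits extra patients without committing to them.

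**Dropout may be below 20%.** The protocol limits missing endpoints. Section 6.1 classifies the outcome from examination or imaging alone, section 7.2 excludes patients unwilling to return, section 13.1 requires three contact attempts, and section 10.3 allows register data. This point stands in part: 16.3% dropout would absorb 5% exclusion, and 11.7% would absorb 10%. But 20% is the protocol's own planning assumption, and the stated power should hold under it.

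**The larger losses rest on assumed rates.** This is true. Planned ostomy, metastatic malignancy, relaparotomy and incarcerated hernia are screened out before randomisation, so the residual rate may be low. Yet inclusion is open to any gastrointestinal indication, and an unplanned ostomy, an open abdomen or a newly found malignancy is by nature known only during surgery.

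**The assumed effect is cautious.** The two studies cited in section 2.4 report 28.6% v 3.2% and 33.3% v 5.9%. Even with 68 per group, exact power for differences of that size is about 99%. Both studies are non-randomised, however, and the trial chose to be powered for 25% v 10%; that is the claim being checked.

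**Recalculation is available.** It is optional and refers to dropout alone. The two-year dropout rate matures only two years after surgery, while enrolment lasts about 24 months, so the trigger becomes informative as recruitment closes.

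**Conclusion.** The concern holds. The figures 97, 122 and 244 are computed correctly, but the 20% inflation is used up by loss to follow-up, and nothing is set aside for patients removed during surgery. With 244 randomised and 20% dropout, the stated 80% power tolerates about one exclusion in the whole trial.

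The size depends on a rate the protocol does not give. The loss is under 3 percentage points up to 5% exclusion, about 5 points at 10% and about 9 points at 20%. These figures assume that 244 counts patients before exclusion, that dropout is 20% of those remaining, and that exclusions fall equally on both groups. This should be fixed, but it does not undermine the design.

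**What to change.** Keep 244 randomised and amend section 19.1 and the synopsis to:

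1. Say that 244 counts patients before intra-operative exclusion.
2. State an assumed exclusion rate, marked as an assumption, and the power that results, for example 87 evaluable per group and 75% at 10%.
3. Extend the recalculation trigger to total attrition, pooled over both groups and assessed blind, counting intra-operative exclusions as well as dropout. The margin is 244 − 194 = 50 patients, or 20.5%. Exclusions are known on the day of surgery, so this part of the trigger can act while recruitment is still open.

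This costs protocol wording only, and the power quoted becomes less favourable.

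If the sponsor means to have 97 evaluable per group after both losses, 19.1 should say so and give the larger number to be randomised: 256 at 5%, 270 at 10%, 304 at 20% or 348 at 30%. That is a real recruitment cost of 12, 26, 60 or 104 more patients. If exactly 122 per group must remain after exclusion, each total rises by two.

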### 19.2 Allocation

Patients having emergency midline laparotomy for any indication and fulfilling the inclusion criteria will be randomized prior to surgery after informed consent is signed. Patients are randomly

allocated (1:1 ratio) either to an intervention group or a control group according to a computer-

generated list compiled by a biostatistician otherwise uninvolved in the clinical care of trial patients. Allocation will be stratified according to BMI ( $<30$  and  $\geq 30\text{kg/m}^2$ ), history of previous

laparotomy and age ( $<65$  and  $\geq 65$ - years) and-blocked within strata using random permuted blocks (block size 2, 4, 6 and 8). A separate randomization list will be created for each participating

center. All patients who have an emergency midline laparotomy during randomization period are assessed for eligibility.

### 19.3 Endpoint analysis

All analyses will be performed primarily according to modified intention to treat (ITT) principle.

Patients who fulfill exclusion criteria intraoperatively (after randomization) will not be included in the analyses. Per protocol analyses will be used as safeguard against the risk of falsely claiming

PREEMER TRIAL 30

equality/superiority. The primary endpoint will be the incidence difference of IHs with 95% confidence interval between the study groups during 2-years follow up. Secondary outcomes are

listed previously. The primary endpoint as well as other categorical data will be analyzed by the  $\chi^2$ - test or Fisher's exact test. Student's t-test or Welch test will be used for continuous variable, the

latter if assumption of homogenous variances does not hold. The incidence of hernia will also be

analyzed using Kaplan-Meier analysis.

The linear mixed model (LMM) or generalized linear mixed model (GLMM) will be used for repeatedly measured data, the previous for continuous data and latter for categorical data. Multiple imputations of missing outcome data will be used for sensitivity analyses.

Prospectively

planned subgroup analyses are as follows: BMI>30, previous hernia and contamination class 4.

However, sample size calculation is done only for the primary end point and subgroup analyses are hypothesis generating only. The statistical programs SPSS (IBM Corp.

Released 2016. IBM SPSS

Statistics for Windows, Version 24.0. Armonk, NY: IBM Corp) and SAS (version 9.4, SAS Institute Inc., Cary, NC, USA) will be used for the analyses.

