- Indication for laparotomy is incarcerated hernia
- Pregnant or suspected pregnancy
- <18 years
- Metastatic malignancy of any origin
- Planned ostomy
- Patients living geographically distant and/or unwilling to return for follow-ups
- No informed consent
- Subject participates in another RCT

Intra-operative exclusion criteria applicable for both randomization groups

- Abdomen is left open
- Second look laparotomy planned
- Inability to keep the mesh securely out of the peritoneal cavity or close the anterior fascia
- Intra-abdominal malignancy diagnosed at the operation
- >2 cm hernia in midline
- Ostomy made at the operation

Human Subjects Protection	
Full approval of Ethical Committee of Oulu University Hospital approved by Institutional revision board in each participating hospital, with all other specific approvals, must be obtained for the study prior to study initiation at the site. Subjects must sign an EC-approved Informed Consent Form (ICF) prior to enrollment into this study.
 
As the previous research on synthetic mesh utilized as prophylaxis at emergency laparotomies is scarce, an analysis of the complications and risks will be evaluated for safety reasons after 30 patients have been randomized to both groups and reached 30 days follow-up. For the same reason, there will be further analysis on the complications of the mesh

---------------------------	---

	after 30 patients randomized to each group have reached the 2 years follow-up.

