#### 14.2 Wound Closure technique

At the end of the operation, the abdomen will be closed according to patient's randomization group if applicable.

In the mesh group, the posterior layer of rectus sheath is opened as close to midline as possible

without interrupting the midline. The space behind the rectus muscle is created mainly using blunt dissection. At each ends of the incision, opening of the retrorectus space is reached both cranial

and caudal over the ends of the wound, if applicable. The posterior layer is closed using 0 or 2-0

slowly absorbable monofilament 4:1 small stitch technique. The stitch bites are 5 mm with 5mm

interstitch space. The length of the wound is measured, as well as the length of suturing material

used. The aim is to close using suture material at least four times the length of the wound (4:1) by small stitch technique. After securing there will be no contact with the mesh and abdominal

cavity, 8 cm wide self-gripping mesh (Progrip™, Medtronic) is applied on the posterior layer of the rectus sheath, reaching over the opening at each end. The anterior layer of rectus sheath is closed using slowly absorbable monofilament USP 2-0 or 0 suture by 4:1 small stitch technique. The

length of the mesh and suture material used are measured. Subcutaneous layer will be left open if contamination class is 4. The subcutaneous layer may be left temporary with VAC or other wound dressing according to surgeons' preference. In contamination classes 1-3, the skin is closed

according to surgeons' preference.

In case the mesh cannot be safely kept outside the abdominal cavity, patient is intra-operatively excluded.

PREEMER TRIAL 27

In the no mesh group, the rectus aponeurosis is closed in a single aponeurotic layer by using slowly absorbable monofilament USP 2-0 or 0 suture by 4:1 small stitch technique. Both the length of the wound and length of the suture material used is measured.

Catalogue of the operative technique will be sent to all participating surgeons to standardize the procedure.

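### The mesh-containment exclusion is headed as applying to both groups, but section 14.2 describes a check only in the mesh arm, and 19.3 then drops these randomised patients from the primary analysis

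*Protocol*

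**What the plan says.** Section 19.2 places randomisation before the operation: patients who meet the "criteria will be randomized prior to surgery after informed consent is signed". The synopsis and section 7.2 then list six intra-operative exclusions under the heading "Intra-operative exclusion criteria applicable for both randomization groups". One of the six has two limbs: "Inability to keep the mesh securely out of the peritoneal cavity or close the anterior fascia".

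Section 14.2 sets out closure by group. The mesh group has retrorectus dissection, closure of the posterior layer, confirmation that mesh and abdominal cavity are separated, and then mesh placement. That account ends with the sentence "In case the mesh cannot be safely kept outside the abdominal cavity, patient is intra-operatively excluded". The control text follows: "In the no mesh group, the rectus aponeurosis is closed in a single aponeurotic layer". It mentions no retrorectus space, no separate posterior layer and no containment judgement.

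Section 19.3 makes modified ITT the primary principle and says "Patients who fulfill exclusion criteria intraoperatively (after randomization) will not be included in the analyses". It names two further analyses: per protocol, and multiple imputation ("Multiple imputations of missing outcome data will be used for sensitivity analyses"). It names no analysis of all randomised patients.

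**The concern.** A modified ITT set keeps the protection of randomisation when the reason for removal can arise and be recognised equally in both arms. For the containment limb, the protocol gives a means of recognising it in one arm only, after allocation and as a result of attempting the allocated treatment. A mesh patient in whom placement fails leaves the analysis. A control with the same anatomy has a single-layer closure and stays. For this limb, the primary comparison is then between mesh patients in whom placement succeeded and all controls.

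The two further analyses are not described as correcting this. Multiple imputation fills missing outcomes of patients in the analysis set, and these patients are outside it. Per protocol is not defined in the document, but it would not ordinarily restore patients who did not receive the mesh. In addition, section 3 makes feasibility part of the objective, and failed placement is a feasibility result that would be absent from the comparison.

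**Working it through.** **The plan's own figure.** Section 19.1 assumes hernia rates of 10% and 25%, α = 0.05 and 80% power. With the two-sided unpooled formula, (1.96 + 0.842)² × (0.10×0.90 + 0.25×0.75) / 0.15² = 96.8, so 97 per group. Dividing by 0.80 for dropout gives 121.25, so 122. Both figures reproduce and the sample size is not in dispute. By exact binomial enumeration of the uncorrected chi-square test, 97 per arm has 80.2% power, and its true level at 25% in both arms is 5.1%.

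**Bias under no true effect.** Let *d* be the share of the mesh arm excluded for failed containment and *r* their 2-year hernia risk. The protocol gives neither, so both are assumptions. If all randomised patients have risk 25%, the remaining mesh patients have risk

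r₀ = (0.25 − d·r) / (1 − d),

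and controls stay at 0.25. Example: d = 0.10 and r = 0.50 give (0.25 − 0.05)/0.90 = 0.2222, a spurious difference of 2.8 points. Type I error is two-sided with 97 analysed per arm; positive differences favour mesh.

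| d | r | r₀ | spurious difference (points) | type I error |
|---|---|---|---|---|
| none | – | 0.2500 | 0 | 5.1% |
| 2% | 50% | 0.2449 | 0.5 | 5.2% |
| 2% | 60% | 0.2429 | 0.7 | 5.2% |
| 5% | 15% | 0.2553 | −0.5 | 5.2% |
| 5% | 30% | 0.2474 | 0.3 | 5.1% |
| 5% | 50% | 0.2368 | 1.3 | 5.6% |
| 5% | 60% | 0.2316 | 1.8 | 6.1% |
| 10% | 15% | 0.2611 | −1.1 | 5.4% |
| 10% | 25% | 0.2500 | 0 | 5.1% |
| 10% | 40% | 0.2333 | 1.7 | 5.9% |
| 10% | 50% | 0.2222 | 2.8 | 7.5% |
| 10% | 60% | 0.2111 | 3.9 | 10.0% |

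Type I error first reaches 6% at a risk of about 58% when 5% are excluded and about 41% when 10% are. With 2% excluded it never does.

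**Power if these patients are kept.** Assume a relative risk of 0.4 (10%/25%) where mesh is placed and no effect where it is not. The all-randomised mesh risk is d·r + (1 − d)·0.4·r₀, compared with 25% at 97 per arm. The modified ITT figures assume that excluded patients are not replaced, which leaves 95, 92 or 87 mesh patients against 97 controls.

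| d | r | all-randomised mesh risk | power, all randomised | power, modified ITT |
|---|---|---|---|---|
| 2% | 25% | 0.1030 | 78% | 80% |
| 5% | 25% | 0.1075 | 75% | 79% |
| 10% | 25% | 0.1150 | 70% | 78% |
| 5% | 50% | 0.1150 | 70% | 82% |
| 10% | 50% | 0.1300 | 58% | 85% |
| 10% | 60% | 0.1360 | 53% | 87% |

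In the last three rows, part of the modified ITT power comes from the same selection that produces the bias. Those figures are not a fair benchmark.

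**The case against.** The strongest reply is that one-sidedness is an inference. The heading twice claims both groups, the exclusion sentence in 14.2 refers to the patient without naming an arm, and the section opens by making closure by allocation conditional on applicability. A surgeon could judge hypothetically, in a control, whether a mesh could have been contained. This stands in part: the text shows an intent of symmetry and does not say that controls are never excluded. But it describes no step by which that intent could be met. Confidence is therefore high that the described procedure is one-sided, and moderate that it acts so in practice.

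A second reply is that the likely harm is small. That also stands: material inflation needs both frequent failure and a risk well above 25%, and the protocol points to neither.

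A third is that an all-randomised primary analysis loses power, sharply in the high-risk cases. That is correct. It is why an all-randomised sensitivity analysis is acceptable as a minimum.

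A reader might also infer more than the documents support:
- **That the trial is biased towards mesh.** The direction depends on an unknown risk.
- **That all the intra-operative exclusions are at fault.** The anterior-fascia limb and the other five criteria can arise in either arm.
- **That 9.1 is contradicted.** Its 30 patients per group set the timing of the safety review, and the text does not say whether failed placements count.
- **That the per protocol role ("Per protocol analyses will be used as safeguard against the risk of falsely claiming" equality or superiority) is itself an error.** That set is not defined here and may be defined elsewhere.

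**Conclusion.** The point holds for the containment limb only. The both-groups heading and the procedure in 14.2 do not match, and 19.3 turns that mismatch into removal of randomised patients from the primary analysis. A statistical analysis plan that kept them would contradict the rule 19.3 sets.

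The resulting bias is possible, but its size and sign are unknown. Under the assumptions above (no effect, 25% control rate, 97 analysed per arm) it is negligible at 2% excluded and at most 1.3 points at 5% excluded with risks from 25% to 50%. It becomes material, at 2.8 points and 7.5% type I error, at 10% excluded with 50% risk. The planned difference is 15 points. The point should be fixed because the correction is simple and removes a dependence on an event described as observable in one arm. It is not evidence that the result would be wrong.

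**What to change.** **In 19.3:**
- Keep patients who meet only the mesh-containment limb in their randomised arm for the primary analysis, with the planned 2-year clinical and ultrasound assessment.
- Show the current modified ITT as a sensitivity analysis.
- Report these exclusions by arm and reason as a feasibility result.
- As a minimum, if the primary set is not changed, add a sensitivity analysis of all randomised patients.

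**In the synopsis, 7.2 and 14.2:** reconcile the heading with the procedure for this limb, so that it is clear whether and how it is judged in controls.

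No change to 9.1, 19.1, the per protocol wording, the timing of randomisation or clinical handling is needed for this point.

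**Cost:** wording, 2-year assessment of what should be a few patients, and dilution of the effect. If failures carry a 25% risk, the net loss against the modified ITT is about 1, 4 or 8 power points at 2%, 5% or 10% failing, from the unrounded figures. If their risk is higher, all-randomised power falls further, to about 70% (5% failing, 50% risk), 58% (10%, 50%) or 53% (10%, 60%). The sponsor should weigh this when choosing between the full change and the minimum.
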